3.4 Intervention

1. Intervention group: Use the Eyerising RLRL device to treat with the treatment device twice a day, three minutes each time, with an interval of 4 hours. The method of use is as follows:

- A. Put the instrument on a stable desktop, confirm the interface before connecting accessories;
- B. Connect the power supply and turn on the power switch;
- C. Let the user sit in a suitable position, loosen the hand-wheel on the side of the treatment device, and adjust it up and down to the most suitable angle to make the eyes relatively comfortable when resting on the goggles, and fix the hand-wheel to a fixed angle;
- D. Enter the subject's unique account and password, and click Confirm to log in;
- E. After logging in, the first interface enters the photo-kinetic energy treatment item by default, take off the glasses, click OK. Then, making sure that there is visible red light in the eye position corresponding to the instrument, and put the eyes close to the blue eye mask;
- F. For the first use, please place your hands on the top of the treatment device and adjust the interpupillary wheel on the top at the same time. It is better to regard the two light points as one light point. If not, the brightest light also can be used.
- G. After three minutes of use, the light kinetic energy will automatically stop, leave the blue eye mask, close your eyes and rest for 3-5 minutes, until the front and back image spots disappear;

H. After using the instrument, turn it off.

2. Control group: single vision spectacle lenses

3.5 Outcomes

1. Primary Outcome: Change of Axial length (AL, mm) at 12-month follow-up
2. Secondary Outcome: Change of cycloplegic spherical equivalent (SE, D) at 12-month follow-up
3. Optional Indicators:

Changes of uncorrected visual acuity (UCVA), best-corrected visual acuity (BCVA), intraocular pressure, etc.;

Changes of corneal thickness (CT), anterior chamber depth (ACD) and lens thickness (LT);

Observe macula and the structure of fundus around the optic disc;

Observe the choroid/retinal thickness of the fundus;

Compliance index: frequency of equipment uses.

[figure not shown]
3.6 Study sample size

Sample size calculation

The sample size estimation was conducted assuming an α level of 0.05, 90% power, an annual axial elongation of 0.40 mm with a standard deviation of 0.40 mm over 12 months (based on previous results from our study group), and a 50% treatment effect (reducing axial elongation by 0.20 mm). The required sample size was 86 participants per group, totaling 172 participants. After adjusting for a 10% loss to follow-up, the total sample size was 192 participants.

4. FIELD WORK PROCEDURES

4.1 Summary flow chart

4.2 Baseline and Follow-up Examination

1. Baseline examinations

Standardized case report form (CRF) will be administered. The measurements outlined below will be performed at the baseline examination.

1) Registration: Name, date of birth, gender, ethnicity, contact information, and history of ocular disease or surgery, outdoor activities, time and habits of using eyes at close range, history and treatment of myopia, history of general medical conditions, history of allergies, will be obtained from questionnaire interviews and input into the EDC system.

2) Visual acuity: An ETDRS chart (Guangzhou Xieyi Weishikang, Guangzhou, China) with standard illumination will be used to measure distance visual acuity. Visual acuity measurement is performed at a distance of 4 meters. Uncorrected and best corrected visual acuity will be measured.

3) Cover-uncover test: Children will be asked to focus on a near object. The cover-

uncover test will be used to confirm strabismus and determine the type of ocular deviation

4) Ocular biometric measurements via IOL Master: Before cycloplegia, IOL Master (version 5.02, Carl Zeiss, Jena, Germany) is used to measure axial length. Using model eye to calibrate before measurement. Taking the average of 3 consecutive measurements. The difference between any two measurements cannot exceed 0.05mm, otherwise the measurement shall be performed again.

5) Cycloplegia: 1% cyclopentolate hydrochloride (Cyclogyl) is used as a mydriatic agent. Each time, the patient firstly puts 1 drop of Proparacaine Hydrochloride, 1 drop of Cyclogyl after 15 seconds, and 1 drop Cyclogyl 5 minutes later. 45 minutes after the last drop, checking the degree of pupil dilation and light reflection. Dilation and light reflex status will be recorded and full cycloplegia will be justified if the pupil dilates to 6 mm or greater and the light reflex is absent. If the requirements for cycloplegia are not met, the third drop of Cyclogyl will be given. Then the cycloplegia will be reconfirmed after 15 minutes.

6) Cycloplegic auto-refraction: Cycloplegic auto-refraction will be conducted using an auto-refractor (KR-8900, Topcon, Tokyo, Japan). The same auto-refractor will be used throughout the study. It will be calibrated before each examination session to ensure there is no equipment drift during the long follow-up process.

7) Slit-lamp examination: Slit-lamp examination will be used to examine the anterior segment, lens, vitreous, and fundus, and any abnormalities will be recorded.

8) Optical coherence tomography (optional): SS-OCT fundus image acquisition and data processing: using swept source OCT (DRI OCT-1 Atlantis, Topcon) 9 Line Radial follow-up mode to scan and collect images to obtain fundus pictures and fundus tissue tomographic images. Before the collection, the subjects should be asked to sit still for a while, avoid taking coffee and drinks; during collection, doctors should pay attention to correct the axial magnification; researchers should concentrate on collection time to avoid the influence of the time rhythm fluctuation of choroidal thickness. After the choroidal boundary is automatically segmented by the machine's built-in software,

manual verification and correction are carried out, and the choroidal thickness data of 9 regions of the fovea and the inner, middle and outer rings (upper, lower, nasal, and temporal) are obtained.

2. Follow-up Examinations:

- 1) Questionnaire: A questionnaire on adverse events following the intervention will be administered at each follow-up visit and unexpected visits for children in the intervention group. Children and their parents/guardians will be asked about the side effects, including but not limited to short-term glare, flash blindness, and afterimages.
- 2) Visual acuity: An ETDRS chart (Guangzhou Xieyi Weishikang, Guangzhou, China) with standard illumination will be used to measure distance visual acuity. Visual acuity measurement is performed at a distance of 4 meters. Uncorrected visual acuity will be measured for each follow-up visit, best corrected visual acuity will be measured for the baseline, 6-month and 12-month follow-up visit.
- 3) Ocular biometric measurements via IOLMaster: IOLMaster will be used to measure the axial length of both eyes. Five measurements will be taken for each eye. The axial length measurement will be based on the mean of these five values if the desired precision (<0.05 mm) is achieved.
- 4) Cycloplegia: Cycloplegia will be induced with three drops of 1% cyclopentolate administered at the 0, 5th, and 20th minute to each eye. The light reflex and pupil dilation will be checked after an additional 15 minutes. Dilation and light reflex status will be recorded and full cycloplegia will be justified if the pupil dilates to 6 mm or greater and the light reflex is absent.
- 5) Cycloplegic auto-refraction: Cycloplegic auto-refraction will be conducted using an auto-refractor (KR-8800, Topcon, Tokyo, Japan). The same auto-refractor will be used throughout the study. It will be calibrated before each examination session to ensure there is no equipment drift during the long follow-up process.
- 6) Slit-lamp examination: Slit-lamp examination will be used to examine the anterior segment, lens, vitreous, and fundus, and any abnormalities will be recorded.

7) Optical coherence tomography (optional): Swept Source-OCT (DRI OCT-1 Atlantis, Topcon) will be used to capture the macular scan. Shooting mode: 12 mm radial scan mode (follow up mode).

8) Safety assessment

- ① The incidence of allergic reactions;
- ② Afterimage duration exceeds 5 minutes;
- ③ Decreased near visual acuity;
- ④ Levels of side effects such as photophobia and blurred vision;
- ⑤ Increased intraocular pressure, headache, nausea and vomiting, etc.

Follow-up Schedule

(1) Visit 1: Screening period (-7~0 days)

- 1) Sign the "Informed Consent";
- 2) Record the general information of the patient;
- 3) Record the medical history;
- 4) Perform visual inspection, axial inspection, intraocular pressure inspection, equivalent spherical lens measurement, slit lamp inspection, OCT inspection;
- 5) Review the inclusion and exclusion criteria;
- 6) Record the combined/concomitant medication;

(2) Visit 2: Enrolment and randomization (day 0)

- 1) Randomly group, and the intervention group will receive experimental devices;
- 2) Record device defects;
- 3) Record the combined/concomitant medication;

(3) Visit 3: Day 30±14

- 1) Perform visual inspection, axial inspection, and intraocular pressure inspection;
- 2) Record the combined/concomitant medication;
- 3) Record adverse events/device defects.

(4) Visit 4: Day 90±14

- 1) Perform visual inspection, axial inspection, and intraocular pressure inspection;

2) Record the combined/concomitant medication;

3) Record adverse events/device defects.

(5) Visit 5: Day 180±14

1) Perform vision examination, axial examination, intraocular pressure examination, equivalent spherical lens, slit lamp examination, and OCT;

2) Record the combined/concomitant medication;

3) Record adverse events/device defects.

(6) Visit 6: Day 270±14

1) Perform visual inspection, axial inspection, and intraocular pressure inspection;

2) Record the combined/concomitant medication;

3) Record adverse events/device defects.

(7) Visit 7: Day 365±14

1) Perform vision examination, axial examination, intraocular pressure examination, equivalent spherical lens, slit lamp examination, and OCT;

2) Record the combined/concomitant medication;

3) Record adverse events/device defects.

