3.3 Randomization and masking

A statistician without contacts with the participants generated the randomization sequence using SAS software (version 9.4; Cary, NC, USA). All eligible participants were randomly assigned to the intervention (RLRL plus SVS) or control (SVS only) groups at a 1:1 ratio. The randomization process adopted central stratification block randomization with block sizes of four or six. Each eligible participant was assigned a number based on their study entry sequence. Random assignment outcomes were

recorded in sealed envelopes with the corresponding sequential numbers written on the covers. Then, an investigator at the main center took custody of the envelopes. Each time an eligible participant's informed consent was acquired, the investigators responsible for group allocation at the six centers contacted the investigator holding the envelopes by telephone. The investigator immediately opened the envelopes and provided information on the group allocation of the newly enrolled participants. Owing to the nature of the intervention, the participants were aware of their assigned treatment groups. However, outcome assessors, including clinical examination technicians, optometrists, ophthalmologists, and statisticians, were blinded to the treatment allocation.

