5.2 Statistical analysis plan

The intention-to-treat (ITT) population comprised participants randomly assigned to either group. Data from all participants who attended at least one subsequent follow-up visit were included in the analysis, regardless of treatment or follow-up visit compliance. No imputation was used for the missing data. Individuals who switched to other myopia treatment modalities, such as orthokeratology or atropine eye drops, or discontinued the RLRL treatment, were censored. If a participant had only one eye with a SER exceeding -4.0 D, that eye was selected for the statistical analysis. In cases where both eyes were exceeding -4.0 D, the right eye was chosen for the analysis.

Treatment efficacy was assessed using longitudinal mixed models for primary (changes in AL) and secondary (changes in SER and IOP) outcomes at multiple follow-up visits. The mixed effects model was fitted with a random intercept and random slope for the participant, where the group, visit, group-by-visit interaction, baseline age, sex, and baseline AL were fixed effects. Estimated mean treatment differences and corresponding 95% confidence intervals (CIs) were derived from mixed models. UCVA alterations were classified into three categories: decline by two or more lines, stable (within a line), or improvement by two or more lines. The BCVA at the 12-month and baseline was evaluated against the 20/25 standard.

Sensitivity analyses were conducted to assess the treatment effects of therapy in controlling myopia progression, specifically axial elongation and SER progression, across different baseline SER and age groups.

A longitudinal mixed-model analysis was conducted to assess the relationship between treatment efficacy and compliance within the intervention group. Treatment compliance in the intervention group was measured as a percentage of the total number of assigned treatment sessions.

Safety analyses were performed in the ITT population. All adverse events were reported individually. Six ophthalmologists, one from each center, independently scrutinized the OCT scans for potential structural anomalies.

6.MONITORING

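### Side effects are solicited by questionnaire in the RLRL arm only, and the SAP's single BCVA rule, a 20/25 check, is insensitive to change; the OCT label and the two safety lists need reconciling

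*Combined protocol and SAP*

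**What the plan says.** **Eliciting symptoms.** Section 4.2, Follow-up Examinations, item 1: "A questionnaire on adverse events following the intervention will be administered at each follow-up visit and unexpected visits for children in the intervention group". On content it says: "Children and their parents/guardians will be asked about the side effects, including but not limited to short-term glare, flash blindness, and afterimages". For all children, the follow-up schedule for Visits 3 to 7 says "Record adverse events/device defects", with no restriction by arm. The safety list in item 8 of the same section is also unrestricted and includes, for example, "Levels of side effects such as photophobia and blurred vision". Section 5.2 places safety analyses in the ITT population and adds: "All adverse events were reported individually". It names no between-arm comparison of adverse events. Section 3.3 says that "outcome assessors, including clinical examination technicians, optometrists, ophthalmologists, and statisticians, were blinded to the treatment allocation".

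**BCVA.** The Abstract and section 3.5 list change in BCVA among the Optional Indicators. Section 4.2 has it measured at baseline, 6 and 12 months. Section 5.2 has one sentence on it, which sets the baseline and month-12 values against 20/25. The three-way classification by lines lost or gained in section 5.2 is for UCVA alone. Section 3.1 admits children with BCVA as poor as LogMAR 0.2.

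**OCT and safety lists.** Section 4.2 heads the baseline item "Optical coherence tomography (optional): SS-OCT fundus image acquisition and data processing" and the follow-up item "Optical coherence tomography (optional): Swept Source-OCT (DRI OCT-1 Atlantis, Topcon) will be used to capture the macular scan". The visit list and the table in section 4.3 schedule OCT at Visits 1, 5 and 7 without that label. Section 5.2 has six ophthalmologists read the scans. The Abstract's safety list defines retinal structural damage on SS-OCT images; item 8 of section 4.2 has no such entry.

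**The concern.** Safety is half of the stated purpose. A child who is asked about glare at every visit will report more of it than a child who is not asked, even if both have it equally often. If prompted reports from one arm are set beside reports of unspecified origin from the other, the difference mixes a device effect with a questioning effect.

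The BCVA point is one of sensitivity. A level check at two times can stay silent while a child loses two lines, which is the loss the SAP treats as a decline for UCVA. UCVA is a poor substitute because myopia progression itself changes it.

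The OCT and list points concern completeness. A site could take the label as leave not to scan, and staff working from one list could overlook items that appear only in the other.

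**Working it through.** **1. Denominator.** Section 3.6 gives alpha 0.05 (taken as two-sided), power 90%, SD 0.40 mm and difference 0.20 mm. The normal approximation is n = 2 × (1.960 + 1.282)² × 0.40² / 0.20² = 84.1, so 85 per group. The t-test solution is 85.03, so 86, which is the plan's figure. 86 / 0.90 = 95.6, so 96 per arm and 192 in total. The plan's figures reproduce, and 96 is used below.

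**2. Solicitation.** Visits 3 to 7 are five follow-up visits.
- RLRL: 5 questionnaires per child; 96 × 5 = 480 at full attendance. This is the scheduled count and not a ceiling, because unscheduled visits add to it.
- Control: 0 per child.

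Of the symptoms named in the questionnaire, glare clearly can occur in both arms. Photophobia, blurred vision and headache are in item 8 of section 4.2. Afterimages belong to treatment sessions and have no control counterpart.

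If the true rate p is equal in both arms, capture is complete under RLRL and a fraction q is captured in controls, the spurious difference is p × (1 − q). The documents give neither p nor q. As an assumption only, p = 10% gives 7.5 points at q = 25%, 5 points at q = 50% and 0 at q = 100%.

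**3. BCVA against 20/25.** log10(25/20) = 0.097, taken as LogMAR 0.1; one line is 0.1. Assume that a child meets the standard at 0.1 or better.

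| Baseline | After two-line loss | Category changes? | Smallest loss that changes it |
|---|---|---|---|
| -0.2 (meets) | 0.0 (meets) | No | 4 lines |
| -0.1 (meets) | 0.1 (meets) | No | 3 lines |
| 0.0 (meets) | 0.2 (fails) | Yes | 2 lines |
| 0.1 (meets) | 0.3 (fails) | Yes | 1 line |
| 0.2 (fails) | 0.4 (fails) | No | None |

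The rule misses a two-line loss from three of these five levels. It also flags a one-line loss from 0.1, which the UCVA rule would call stable. If meeting the standard instead required better than 20/25 (0.0 or better), the missed levels would be -0.2, 0.1 and 0.2, so the problem does not depend on that reading.

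**4. OCT coverage.** With no structural event among n children scanned, the one-sided 95% upper bound is 1 − 0.05^(1/n). It is 3.1% at n = 96, 3.4% at n = 86 and 6.1% at n = 48. If 5% were chosen as a benchmark, which is an assumption with no source in the documents, 59 scans would be needed (bound 4.95%; 58 gives 5.03%), or 59/96 = 61% of the arm.

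**5. Safety lists side by side.**
- Abstract only: sudden loss of vision, glare, flickering, retinal structural damage.
- Section 4.2 item 8 only: allergic reactions, reduced near acuity, blurred vision, headache, nausea, vomiting.
- Both: afterimage beyond 5 minutes, photophobia, raised intraocular pressure.

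Sections 4.2 and 4.3 describe and schedule distance acuity only, so the near-acuity item has no measurement behind it.

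**The case against.** The best defence of the questionnaire is that it is a device form for device users. Its named items closely match the laser reactions in the device precautions, and only glare among them plainly applies to spectacle wearers. That stands as a reason to keep session-linked items for RLRL alone. It does not explain why shared symptoms have no stated route of questioning in controls.

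A reader might infer that adverse events are not collected in controls. The documents do not support this: recording at Visits 3 to 7 and the item 8 list cover both arms, and what is missing is the method of asking. A reader might also infer a high chance of a falsely significant excess under RLRL. That would need almost no capture in controls and a between-arm test, and the plan supports neither. Nor would this bias conceal harm from the device, since it runs the other way.

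On BCVA, applying 20/25 at both baseline and month 12 does show who crosses it, so it would be wrong to say that the rule shows no change at all. Sudden loss of vision and individually reported events are a further route to detection, but not one designed for gradual change.

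On OCT, the label may only mark endpoint rank. Intraocular pressure is also an Optional Indicator, yet it is ticked at every follow-up visit and analysed as a secondary outcome. Slit-lamp fundus examination at the same visits is a partial backstop. Both safety lists end in an open et cetera, so neither claims to be complete. These points stand and reduce the OCT and list issues to reconciliation.

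**Conclusion.** Two points should be fixed, and one is minor.

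- **Elicitation.** The imbalance is certain on the text (5 scheduled questionnaires against 0). The resulting bias is of unknown size, because the documents give no symptom rate and no capture fraction for controls. It affects how reported events are read and not a tested result.
- **BCVA.** The 20/25 check shows threshold crossings but is insensitive to change, and month-6 BCVA has no stated analysis although change in BCVA is a listed indicator. This rests on one line being 0.1 LogMAR and 20/25 being 0.1. No BCVA distribution is given, so the share of children affected is unknown. The weakness applies to both arms and does not favour either.
- **OCT label and safety lists.** These are inconsistencies of wording. A reader might infer that scans were skipped; no passage says so, and actual coverage is not given.

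The primary outcome and the sample size are untouched.

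**What to change.** **Elicitation.** Give the same symptom questions, without session-only items, to both arms at the existing visits. They should be asked by staff who are not masked outcome assessors, and the answers kept from those assessors. The documents do not say who gives the form now, so the protocol should name the role. Report afterimages and other session-linked items for RLRL only. Cost: about 96 × 5 = 480 short forms in controls and some staff time. The SAP is written in the past tense; if follow-up is complete, state the unequal solicitation as a limitation, at no cost.

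**BCVA.** In section 5.2, apply the existing two-or-more-line classification to BCVA change from baseline at 6 and 12 months, by arm, and keep 20/25 as descriptive. No new measurement is needed. Label the analysis post hoc if the data have already been analysed.

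**Reconciliation.** Give OCT one status across sections 4.2, 4.3 and 5.2 and the Abstract. Merge the two safety lists, and remove or explain the near-acuity item without adding a test. Report the number of children scanned per arm at each visit with the zero-event upper bound, and declare any benchmark such as 5% as an assumption. Cost: wording and one reporting table.

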4.3 Process of the practice

Schedule of events table

Phase	Period of Filter	Enrollment and randomization	Period of Treatment				
Visit Time	Visit 1	Visit 2	Visit 3	Visit 4	Visit 5	Visit 6	Visit 7
Observed Time Point	Day-7~0	Day 0	Day 30±14	Day 90±14	Day 180±14	Day 270±14	Day 365±14 天
Demographic data	√						
History-taking	√						
Examination of Distant Vision	√		√	√	√	√	√
Examination of Axial	√		√	√	√	√	√

Intraocular Pressure (IOP)	✓		✓	✓	✓	✓	✓
Spherical Equivalent (SE)	✓				✓		✓
Examination with Slit-lamp	✓				✓		✓
OCT	✓				✓		✓
Sign Informed Consent	✓						
Determine Inclusion/Exclusion Criteria	✓						
Random Grouping	✓						
Distribute Equipment		✓					
Record Device Defects		✓	✓	✓	✓	✓	✓
Record Concomitant Medications	✓		✓	✓	✓	✓	✓
Record Adverse Events	✓		✓	✓	✓	✓	✓
End of Practice							✓

5. Data entry and Analysis

